### 5 SAMPLE SIZE

## 6 RANDOMIZATION

Using an Interactive Web Response System (IWRS), on D1, the site staff or research pharmacist will contact the IWRS after the Investigator has confirmed that the subject fulfills all the inclusion/exclusion criteria. The IWRS will assign a randomization number to the subject, which will be used to link the subject to a treatment arm. The research pharmacist will prepare the appropriate IP and deliver it to study staff in preparation for injection.

A randomization schedule will be employed to facilitate effective randomization and allocation concealment. The schedule will involve a block randomization technique, randomly assigning participants within blocks based on a 1:1 allocation ratio. The randomization schedule will be stratified by study site.

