### **7.3.10 Randomization Strata**

As described in [Section 6](#), randomization is stratified by study site. Furthermore, protocol indicates that analysis will include adjustment for study site. There are approximately 45 study sites and it is likely that some of these study sites will have small number of subjects that are

included in the mITT population and thus could lead to unreliable treatment effects estimates and p-values. With this, the study sites will be pooled by state and then by region. However, if a state has significantly large number of subjects (eg almost double) compared to the other regions, it will be considered as one of the final pooled sites. The resulting final pooled sites (referred to as 'site' from here on) are as follows:

[REDACTED]

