## 7.12 Efficacy Analyses

All statistical tests will be performed using a two-tailed 5% overall significance level, unless otherwise stated. All comparisons between treatments will be reported with 95% confidence intervals (CI) for the difference. Pain profiles through the first four weeks will be presented by the treatment received for the first injection (SP-102, Placebo). Moreover, pain profiles through 12 weeks will be presented by treatment received for second injection (SP-102/SP-102, PBO/SP-102, SP-102/none, PBO/none). Also, the ‘site’ indicated in this section refers to the final pooled sites as described in [Section 7.2.10](#).

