#### **7.12.6.3 Proportion of subjects receiving repeat injection.**

The proportion of subjects receiving repeat injections will be compared between the two treatment groups using a Chi-Square test. The proportion of subjects receiving a repeat injection will be summarized by treatment group.

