#### **7.12.6.15 Proportion of subjects requiring rescue medication**

The proportion of subjects requiring rescue medications will be compared across treatment arms using a Chi-Square test. This endpoint will be analyzed separately for the first 4 weeks (two groups), and the first 12 weeks (four groups).

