#### **7.12.6.16 Percent of rescue medication free days.**

The percent of rescue medication free days will be calculated for the primary efficacy endpoint completers as:

$$\frac{\text{Number of days without rescue medication from baseline to subject's Day 29th in the study}}{28} \times 100$$

For subjects that withdrew from the study prior to the subject's Day 29th in the study, the percent of rescue medication free days will be calculated as:

$$\frac{\text{Number of days without rescue medication from baseline to Early Termination Date}}{\text{Number of days from baseline to Early Termination Date}} \times 100$$

This will be analyzed for the primary analysis period. A one-way ANOVA model will be used to test the difference between SP-102 and the placebo arms.

**7.12.6.17 The mean change from Baseline (D1) to Week 2, Week 4, Week 8, and Week 12 in the mean morning (AM) NPRS average pain score in the affected leg**

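### Three two-group secondary comparisons (repeat-injection proportion, 4-week rescue proportion, rescue-free days) have no analysis adjusted for site, the randomization stratum, so they may be mildly conservative

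*SAP*

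**What the plan says.** SAP section 6: "The randomization schedule will be stratified by study site", with blocks, "randomly assigning participants within blocks based on a 1:1 allocation ratio". PCS group is not a stratum. SAP 7.3.10 notes that "There are approximately 45 study sites", records that the protocol intends adjustment for study site, and pools sites by state and region for use in the models.

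The three comparisons at issue are:

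- Repeat-injection proportion (SAP 7.12.6.3): it "will be compared between the two treatment groups using a Chi-Square test".
- Rescue proportion (SAP 7.12.6.15): "The proportion of subjects requiring rescue medications will be compared across treatment arms using a Chi-Square test". This is done at 4 weeks on the two randomized groups and at 12 weeks on four groups.
- Percent of rescue-free days (SAP 7.12.6.16): "A one-way ANOVA model will be used to test the difference between SP-102 and the placebo arms".

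None has a site or PCS term, and none has an adjusted companion model. SAP 7.12 sets the general rules: "All statistical tests will be performed using a two-tailed 5% overall significance level, unless otherwise stated", and "All comparisons between treatments will be reported with 95% confidence intervals (CI) for the difference". The three sections name no interval method.

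**The concern.** The SAP treats the same data in two ways. Time to repeat injection (7.12.6.2) uses a Cox model with site and PCS; the proportion formed from the same events does not adjust. Cumulative rescue use (7.12.6.13) has an ANOVA with pooled site and PCS group. Time to first rescue (7.12.6.14) follows the repeat-injection Cox approach, through a cross-reference numbered 7.11.6.2 that I read as 7.12.6.2. Rescue proportion and rescue-free days come from the same rescue records and carry no covariates. PGIC, CGIC and the 30/50/75% responder endpoints also have chi-square tests, but each adds a logistic model with site and PCS. The visible part of SAP section 11 gives no reason for the difference.

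Stratified randomization balances the arms within site. If site predicts the outcome, that balance reduces the true variance of the treatment difference, and an analysis that ignores site does not credit the reduction. What is at stake is some power. SAP 7.12.6.19 puts the other secondary endpoints in a sequential procedure that stops at the first non-significant result, so power lost at one step can affect later ones.

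**Working it through.** The documents give no power, SD, event rate or site effect for these endpoints, and the sample-size sections are blacked out. There is no stated figure to reproduce.

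**Inputs from the documents.** Two-sided alpha 0.05 (SAP 7.12); 1:1 blocked allocation stratified by site (SAP 6); about 45 sites (SAP 7.3.10); about 400 randomized (protocol synopsis).

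**Assumed.** R², the share of outcome variance explained by site, shown as a range.

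**Analytic check.** Ratio of unadjusted to correct SE: f = 1/√(1 − R²). Actual alpha of the unadjusted test: 2[1 − Φ(1.960 f)]. If the adjusted test has 80% power, its standardized effect is 1.960 + 0.842 = 2.802, and the unadjusted test has power Φ(2.802 − 1.960 f). At R² = 0.05, f = 1.026 and Φ(2.802 − 2.011) = Φ(0.791) = 78.5%.

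| R² (assumed) | f | Actual alpha | Unadjusted power |
|---|---|---|---|
| 0 | 1.000 | 0.0500 | 80.0% |
| 0.02 | 1.010 | 0.0477 | 79.4% |
| 0.05 | 1.026 | 0.0443 | 78.5% |
| 0.10 | 1.054 | 0.0388 | 76.9% |
| 0.20 | 1.118 | 0.0284 | 72.9% |

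This formula is for a continuous outcome and full adjustment for the stratum.

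**Simulation under the null.** N = 400 and 45 sites. Assumed: blocks of 4, six pooled sites, half the site variance lying between pooled sites, and PCS ≥30 in 30% of subjects. 3000 trials per setting, outcome SD 1. Monte Carlo error is about √(0.05 × 0.95/3000) = 0.4 points for a 5% rejection rate, and about 1/√6000 = 1.3% for an observed SD.

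| Site ICC | PCS R² | One-way ANOVA SE | True SD | Ratio | Type I error |
|---|---|---|---|---|---|
| 0 | 0 | 0.1000 | 0.1005 | 0.995 | 5.1% |
| 0.05 | 0 | 0.0997 | 0.0972 | 1.026 | 4.3% |
| 0.10 | 0 | 0.0994 | 0.0944 | 1.053 | 3.6% |
| 0 | 0.05 | 0.1000 | 0.1013 | 0.987 | 5.6% |
| 0.20 | 0.05 | 0.0990 | 0.0913 | 1.084 | 3.6% |

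The fourth row isolates PCS. With no site effect, the unadjusted SE is correct within simulation error. Adjusting for pooled site and PCS lowers it to 0.0977, which is a gain in precision and not the correction of a wrong SE.

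Pooled site recovers only part of the excess. In the last row, the SE is 0.0990 unadjusted, 0.0917 with pooled site and PCS, and 0.0871 with all 45 sites and PCS.

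**Proportions** (ICC 0.10, PCS R² 0.05). The chi-square SE of the risk difference is 0.0488 against a true SD of 0.0470 (ratio 1.038), with type I error 4.1%. The adjusted risk-difference SE is 0.0474. Under logistic regression, the log-odds-ratio SE rises from 0.2055 to 0.2143, so that interval widens.

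**Power for the proportions.** A second simulation used N = 400, 45 sites, an assumed log odds ratio of 0.65 and otherwise similar assumptions. It compared chi-square with logistic regression that also included baseline pain; R² here is the overall explained variance.

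| R² (approx.) | Chi-square | Adjusted logistic | Gain |
|---|---|---|---|
| 0.03 | 87.6% | 88.1% | 0.5 points |
| 0.08 | 84.5% | 86.0% | 1.5 points |
| 0.14 | 80.8% | 83.9% | 3.1 points |

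Each power carries Monte Carlo error of about √(0.85 × 0.15/3000) = 0.65 points, so the smallest gain is within noise if the two figures are treated as independent. Null error of the adjusted test was 4.1–5.5%.

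**The case against.** The strongest defence is that nothing here is invalid. The tests hold their level, adjusted analyses of the same constructs already exist (time to repeat injection, cumulative rescue, time to first rescue), and the protocol's own rule for secondary analyses (5.2.8.4) is blacked out, so SAP 7.3.10's remark about site adjustment cannot be tied to these endpoints. All of that stands. It limits the size of the point, but does not explain why these comparisons lack an adjusted analysis.

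A reader might also infer more than the documents support:

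- *That the intervals are too wide as a matter of fact.* This depends on how strongly site predicts these outcomes, which the documents do not show. At R² = 0 there is no excess.
- *That omitting PCS group or baseline leg pain also inflates the SE.* Neither is a stratum, so omitting them leaves the stated SE honest. Baseline pain is optional in any case: the cumulative-rescue, time-to-repeat, PGIC and CGIC models omit it.
- *That these three tests alone are unadjusted.* The log-rank comparison in the continuous responder analysis (7.12.6.10) lists no covariates either, and PGIC, CGIC and the responder endpoints begin with plain chi-square tests.
- *That a miss here stops the whole sequence.* The order in 7.12.6.19 is blacked out. If it followed the 18 entries in SAP 4.3, which is only an inference, repeat-injection proportion would be third with 15 entries after it, rescue proportion would have three after it, and rescue-free days two.

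**Conclusion.** The point holds as a low-cost improvement in consistency and efficiency. The two-group comparisons in 7.12.6.3, 7.12.6.15 (4 weeks) and 7.12.6.16 have no analysis by the randomization stratum, unlike the sister endpoints in 7.12.6.2, 7.12.6.13 and 7.12.6.14. Any error is on the conservative side, and the gain to expect is modest. Its size rests on assumed site effects, and the power figures for the proportions come from a model that also included baseline pain. The effect on later tests in the sequence is unknown. The 12-week rescue proportion is outside this point: its four groups depend on later receipt of a repeat injection and are not randomized, so selection is the issue there, not width.

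**What to change.** For 7.12.6.3 and the 4-week comparison in 7.12.6.15, make the deciding test a Cochran-Mantel-Haenszel test or a standardized risk difference stratified by pooled site and PCS group, and report its 95% CI. Adjusted logistic regression is acceptable for the test but will not narrow the log-odds interval.

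For 7.12.6.16, replace the one-way ANOVA with the model in 7.12.6.13 (treatment, pooled site, PCS group), optionally adding baseline mean NPRS average leg pain. If the unadjusted tests are kept, the SAP should say why.

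The cost is a few lines of SAP wording, settled before unblinding. The covariates are collected, and the SAP already specifies the same model terms for neighbouring endpoints.

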**7.12.6.19 Multiplicity**

To control for multiplicity, a sequential testing procedure will be used on the key secondary and other secondary endpoints. Thus, if the primary endpoint is statistically significant, then the key secondary endpoint can be tested. Then if the key secondary endpoint is statistically significant, then the next secondary endpoint can be tested. This will continue until all endpoints have been tested, or until non-significance is observed for an endpoint. The ordering of the tests will follow the order the endpoints listed below:

[Redacted text block containing multiple paragraphs of obscured content]

#### 7.12.6.20 Placebo Responder Analysis

An analysis predicting the placebo response may be performed. Full details will be provided in a separate SAP.

### 7.13 Safety Analyses

The safety analyses will be presented in two ways:

- 1) by the two treatment groups received in the first four weeks for the primary analysis period
- 2) by the four treatment groups for the data up to 24 weeks for the secondary analysis period

All safety analyses will be done in the Safety Analysis Population.

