Each subject will have the option of receiving 1 supplemental OL TF injection of SP-102 ("repeat injection"). To qualify for the repeat injection, subjects must meet Repeat Injection Inclusion Criteria, NPRS pain score in the affected leg, and investigator judgment, which includes a safety evaluation demonstrating no signs or symptoms of adrenal suppression or other safety concerns. The repeat injection may be administered between Weeks (W) 4 and 20. Eligible subjects will receive OL SP-102 repeat injection regardless of their initial treatment assignment (SP-102 or placebo).

In case of inadequate control of radicular pain, up to [REDACTED] will be allowed per day. The subject should be instructed to avoid use of acetaminophen within 6 hours prior to recording an NPRS score. Doses of rescue medication and time taken will be collected in the eDiaries until W12 and thereafter as a concomitant medication.

The subject will complete the eDiary twice daily approximately 12 hours apart (± 2 hours) to record their NPRS scores for pain in the previous 12 hours for 12 weeks following index injection. Thereafter, NPRS scores will be recorded at clinic visits.

All subjects will be seen at the clinic on D15, and every 4 weeks (ie, W4 [D29], W8 [D57], W12 [D85], W16 [D113], W20 [D141], and W24 [D169]) after the DB index injection for up to 24 weeks. Subjects receiving the OL repeat SP-102 injection will also be seen at the clinic 14 days after the repeat injection and continue the DB planned visits as well. The subject will also be contacted by telephone by the site staff 2 days after each IP injection to discuss their progress, any medications they are taking, and if they have had any adverse events (AEs).

The study visits and the planned efficacy analysis after all enrolled subjects have completed W12 are depicted in [Figure 3.1](#).

Figure 3.1: Study Schematic

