3.3.3 Stopping Rules

A single occurrence of an adverse event of special interest (AESI) precludes the subject receiving a repeat injection. Three occurrences of the AESI of the same type across the study will trigger stopping of all further dosing until implementation of a safety review.

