5.2.8.5 Multiplicity

5.2.9 Safety Analyses

Safety endpoints are:

- AEs, compared between 4 groups receiving one SP-102 injection, two SP-102 injections, placebo followed by SP-102 repeat injection, or placebo only.
- Change from Baseline (D1) in laboratory parameters.
- Change from Baseline (D1) in vital signs.
- Change from Baseline (D1) in neurological examination.

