#### 7.4 Conventions

All data listings, summaries, figures and statistical analyses will be generated using SAS version 9.4 or higher.

Subjects will be randomized to 1 of 2 treatment groups (SP-102 or placebo) and will receive 1 injection at Baseline (D1). After 4 weeks, an additional injection of SP-102 may be administered to all subjects regardless of the treatment they were originally randomized to. Because of this, baseline, efficacy, and safety variables will be summarized in two ways.

The first will summarize data for the 2 randomized treatment groups for the primary analysis period. Subjects will be analyzed in either the SP-102 or placebo treatment groups. Baseline summaries and data for this first 4 weeks will be summarized using the following treatment columns. Only baseline data will have the overall column.

SP-102	Placebo	Overall
--------	---------	---------

The second will classify subjects into 1 of 4 groups and will summarize data for the secondary analysis period. These 4 groups include the following:

- Subjects who receive only 1 SP-102 injection
- Subjects who receive 2 SP-102 injections

- Subjects who receive only 1 placebo injection
- Subjects who receive 1 placebo injection and 1 SP-102 injection

The 4 treatment groups will be used in the summary and analyses involving the secondary analysis period (randomization through end of study).

These 4 groups may be combined for additional analyses (eg, combine into one group any subject who received an injection of SP-102 at any point in time).

[REDACTED]

SP-102/SP-102	PBO/SP-102	SP-102/none	PBO/none	Overall
---------------	------------	-------------	----------	---------

Overall columns are to be included within the table shells as follows:

Data	Column labels
Demography	Treatment and overall
Baseline	Treatment and overall
Disposition	Treatment and overall
Prior Medications	Treatment and overall
Concomitant Medications	Treatment and overall
Efficacy	Treatment
AEs	Treatment
Other safety	Treatment

Listings will be sorted in the following order: treatment group, subject, parameter, and visit unless otherwise stated. All data will be listed. Subjects who were not randomized will be displayed after the randomized treatment groups.

Continuous variables will be summarized by the number of non-missing observations, mean, median, standard deviation, and minimum and maximum. For all tabulations of changes from

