- Study medication-related TEAE by system organ class and preferred term, incidence and number of events
- Study procedure-related TEAE by system organ class and preferred term, incidence and number of events
- Serious TEAE by system organ class and preferred term, incidence and number of events
- Serious study medication-related TEAE by system organ class and preferred term, incidence and number of events
- Serious study procedure-related TEAE by system organ class and preferred term, incidence and number of events
- TEAE by system organ class, preferred term and intensity, incidence
- Serious TEAE by system organ class, preferred term and intensity, incidence
- Treatment-related TEAE by system organ class, preferred term and intensity, incidence

- TEAEs leading to early termination of the study by system organ class and preferred term, incidence
- Listing of Serious TEAEs (presented in the Table section of the appendices)
- Listing of Deaths (presented in the Table section of the appendices)

Additionally, an overall summary of the incidence and the number of TEAEs, related TEAEs, SAEs, related SAEs, TEAEs leading to withdrawal, and TEAEs leading to death through 12 weeks, and a summary of incidence and number of events of TEAEs by system organ class and preferred term through 12 weeks will be presented as follows:

- by four groups (SP-102/SP-102, PBO/SP-102, SP-102/none, and PBO/none)
- by treatment (Placebo, SP-102) but only for the subjects in the PBO/SP-102 group
- by exposure to SP-102, that is, Exposed vs. Not Exposed to SP-102; the Exposed group will include the subjects that have received SP-102 for the index injection and/or have a repeat injection while Non-Exposed group will include the subjects that have received Placebo for the index injection and do not have repeat injection

All AEs will be listed.

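### The four-group and Exposed/Not Exposed adverse-event tables sort subjects by a repeat injection that safety findings can block, so they are not treatment comparisons

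*SAP*

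**What the plan says.** Protocol 5.2.9 lists as a safety endpoint "AEs, compared between 4 groups receiving one SP-102 injection, two SP-102 injections, placebo followed by SP-102 repeat injection, or placebo only". SAP 7.13 shows safety data in two ways: by the two treatments for the first four weeks, and "by the four treatment groups for the data up to 24 weeks for the secondary analysis period". SAP 7.4 fixes the period covered: "The 4 treatment groups will be used in the summary and analyses involving the secondary analysis period (randomization through end of study"). SAP 7.13.1 adds Week 12 summaries by the same four groups and by exposure to SP-102, where Not Exposed means placebo at index and no repeat. The overall Week 12 summary has rows for events leading to withdrawal and to death.

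Who may enter a repeat group is set in the protocol. Section 3.1 requires, besides the repeat criteria and the leg pain score, "investigator judgment, which includes a safety evaluation demonstrating no signs or symptoms of adrenal suppression or other safety concerns". Section 3.3.3 adds: "A single occurrence of an adverse event of special interest (AESI) precludes the subject receiving a repeat injection". The rule is the same in both index arms, and the repeat may be given from Week 4 to Week 20. SAP section 2, in describing repeat eligibility, mentions investigator judgment but not the safety evaluation. No visible SAP text warns that the four groups are selected on safety.

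SAP 7.13.1 also plans summaries of treatment-emergent events by treatment, split into the period before and the period after the second injection.

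**The concern.** Group membership is decided at Week 4 or later and depends partly on safety. The events tabulated start at Day 1. An early harm that leads the investigator to refuse the repeat is thus counted, by construction, in SP-102/none or PBO/none. The same holds for anyone who withdraws or dies before a repeat, and that part needs no assumption about how the repeat criteria are applied.

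Evaluating the safety of single and repeat injections is a stated secondary objective. The natural contrast for it, SP-102/SP-102 against SP-102/none, is the one that this sorting distorts: two injections can look safer than one when there is no difference. If the arms take the repeat at different rates, event-free subjects leave one single-injection group faster than the other, so SP-102/none against PBO/none is distorted as well. The Exposed/Not Exposed summary has the same weakness because its Not Exposed group is PBO/none.

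**Working it through.** **Inputs.** The documents give about 400 randomised 1:1, follow-up of 24 weeks, and the repeat window of Weeks 4 to 20. They give no adverse-event rate, no repeat uptake and no frequency of refusal, so there is no plan figure to reproduce. Everything below is an assumption, under a null of no treatment effect on harm.

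Let q be the risk of an early event that can trigger refusal, r the uptake of the repeat among subjects not refused, and b the probability that such an event leads to refusal. The share of subjects with the early event is then:

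- repeat group: q(1-b) / (1-qb)
- no-repeat group: q[1-r(1-b)] / [1-r(1-qb)]

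With a full bar (b = 1) these reduce to 0 and q / [1-r(1-q)].

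**Full bar, equal q in both arms, r = 40% for SP-102 and 60% for placebo:**

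| q | SP-102/SP-102 | SP-102/none | PBO/none | SP-102/none minus PBO/none |
|---|---|---|---|---|
| 0.5% | 0% | 0.005/0.602 = 0.8% | 0.005/0.403 = 1.2% | -0.4 points |
| 2% | 0% | 0.02/0.608 = 3.3% | 0.02/0.412 = 4.9% | -1.6 points |
| 10% | 0% | 0.10/0.64 = 15.6% | 0.10/0.46 = 21.7% | -6.1 points |

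With 40% uptake in both arms and q = 10%, both single-injection groups show 15.6% and the last column is zero. SP-102/SP-102 against SP-102/none is still 0% against 15.6%.

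**Partial bar (b = 0.5, q = 10%, 40%/60%).** SP-102/none 0.08/0.62 = 12.9%; PBO/none 0.07/0.43 = 16.3%; either repeat group 0.05/0.95 = 5.3%.

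**Exposed against Not Exposed (q = 10%, full bar, arms of equal size).** Exposed is the whole SP-102 arm plus PBO/SP-102. At 40%/60% uptake, PBO/SP-102 is 0.9 × 0.6 = 0.54 of the placebo arm, so Exposed shows 0.10/1.54 = 6.5% against 21.7%. At 40% uptake in both arms it shows 0.10/1.36 = 7.4% against 15.6%. This contrast does not need unequal uptake to be distorted.

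**All treatment-emergent events to Week 24.** A simulation used 2,000 trials of 200 per arm, first events at 2% per week, uptake of 45% (SP-102) and 60% (placebo), and 17% dropout spread over 24 weeks. The 17% is back-calculated from the target of 332 Week 4 completers: 1 - 332/400. Incidence in SP-102/SP-102 against SP-102/none was:

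- b = 1: 21.1% against 42.2%
- b = 0.5: 30.0% against 38.2%
- b = 0.25: 33.6% against 36.0%
- b = 0: 37.2% against 33.6%, reversed because dropouts have shorter follow-up

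**What removes it.** In the same simulation at b = 1, the randomised comparison over the first four weeks gave 7.6% in each arm. First-event rates per person-week, with the repeat as a time-varying exposure, were 0.0201 before and 0.0204 after it for SP-102, and 0.0201 and 0.0203 for placebo; the true rate was 0.0200. This check assumed a constant weekly rate.

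**The case against.** The strongest reply is that the gate is softer than it looks. A reader might infer that any safety concern after the index injection bars the repeat. The documents do not say that. Protocol 3.1 asks for an investigator's evaluation, and a mild or resolved event need not lead to refusal. The only explicit permanent bar is an event of special interest, which Protocol 4.2.2 limits to attributable epidural infection or haematoma needing surgery, or paraplegia. The repeat criteria are blacked out. This stands, and it is why low barring risks belong in the range.

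A reader might also infer that the errors always favour SP-102. That is not supported. Higher placebo uptake is an assumption. If barring risks differ, the error can go the other way: at 10% on SP-102 and 2% on placebo with 40%/60% uptake, the groups show 15.6% and 4.9%, a difference of +10.8 points against a true +8.0. Pain-related events may prompt a repeat. With an early risk of 20% and 50% uptake, doubling the odds of a repeat after such an event gives 25.0% in the repeat group and 14.3% in the other. Repeat subjects also have an extra visit and call at which events can be found.

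Nor does the selection survive every person-time analysis. It persists if person-time is assigned to the final four groups, but not when the repeat is time-varying.

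Finally, sound displays are already planned. The four-week two-arm tables and the pre-repeat split avoid the sorting, although crude percentages in the latter still ignore unequal time at risk. The by-treatment tables assign events by onset. SAP 7.4 allows groups to be combined, and the four groups are mutually exclusive, so randomised-arm totals can be recovered. The list of tables is blacked out, so it cannot be said that such a table is absent. No test of adverse events between the four groups is visible. All of this lowers the stakes, but it does not make the whole-period four-group and Exposed/Not Exposed tables comparable, and they carry no visible caveat.

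**Conclusion.** The concern holds for early harms that lead to refusal of the repeat, and for withdrawals and deaths before a repeat: these can appear only in single-injection groups. Two SP-102 injections can therefore look safer than one without any true difference. With unequal uptake, SP-102/none against PBO/none is also distorted; with equal barring risk and higher placebo uptake, this favours SP-102.

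The size cannot be known from the documents. Under a full bar and the assumed 40%/60% uptake, it runs from under half a point at 0.5% barring risk to about 6 points at 10%. For all treatment-emergent events to Week 24 the direction is not settled. Because the comparison appears descriptive, what is at stake is misreading of a stated safety endpoint, not a false-positive rate. It should be corrected because the correction is cheap.

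**What to change.** In SAP 7.13 and 7.13.1:

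1. Add Week 12 and Week 24 tables of treatment-emergent and serious events by randomised index arm. Each is a sum of two existing groups. Name these, with the pre-repeat two-arm table, as the between-arm safety comparison.
2. In the four-group tables, show events with onset before and after the repeat separately. For single against repeat injection, report exposure-adjusted rates with the repeat as a time-varying exposure, and address time since the index injection, since rates may not be constant. A comparator of subjects still eligible at the same visit is less safe: no visible text shows that eligibility is recorded for those who did not repeat.
3. Footnote the four-group and Exposed/Not Exposed tables as non-randomised and not treatment comparisons, because safety findings can keep subjects out of the repeat groups.

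The cost is SAP wording and a few tables built from event and injection dates. No clinical rule changes. One downside is that the later randomised-arm tables include open-label SP-102 in the placebo arm, so they must be read beside the pre-repeat table.
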